4.2 Adherence and protocol deviations

The Intention-to-treat (ITT) population will be used for statistical testing of the primary variables. Hence, anyone who received bottles of cod liver/corn oil will participate in the primary variables' analyses. As a number of bottle shipments were for several reasons returned to sender, such as wrong address, address in another country or did not collect the bottles at the post office despite several urgings, the ITT population is defined as those who had the choice to start taking cod liver/corn oil. Primary variable statistics will also be presented for all who were sent cod liver/corn oils. Participants with missing data on primary variables will be considered as having a negative outcome. Supplementary analyses will be conducted on participants who have reported on the primary variables and on taking oil at given fractions, to be specified when analysing the data, of “the last fortnight”.

5. Trial Population

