6.1 Outcome definitions

Primary variables:

- First primary: Serious COVID-19 (MSIS-confirmed COVID-19 with dyspnoea, hospitalisation, or death)
- Second primary: COVID-19 defined by positive PCR obtained from MSIS
- Third primary: A negative SARS-CoV-2 test (MSIS).
- Fourth primary: Self-reported airways infection

The first incidence of report of any of the above primary variables will be used in the analyses. The specified order will be used for the fallback analyses. The values of all variables will be Yes/No to the condition together with time from one week after start of oil consumption to first reporting of the condition, i.e. Yes (except for third primary variable, where total number of negative tests is reported). Those not reporting a Yes answer, the last reported time will be used as censoring time. The date from one week after oil-consumption starts to the date of reporting of a Yes will be converted to number of days from the first to the second date.

The primary analysis set is the defined ITT sample with missing data on outcome counting as the negative outcome.

Compliance

For sensitivity analyses on compliance, we will define compliant participants as those having taken CLO for at least 2 months. We will also analyse participants based on volume CLO taken (more than 250 ml).

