6.2 Analysis methods

The first, second and fourth primary variables will be analysed for relative risk (risk ratio) of acquiring a condition using cod liver oil versus corn oil using the Wald test³. Time to first occurrence of the primary variables will be plotted using the Kaplan-Meier approach. The third primary variable will be compared for the two treatment groups tested using study duration-adjusted counts. If the use of student's t-test cannot be used due to underlying assumptions not holding up, a median test will be used. If appropriate, the Cox proportional hazard regression will be used to assess the effect of the outcome of the above specified baseline variables on time to occurrence of the primary variables. Otherwise, logistic regression on the occurrence of outcome will be undertaken with the same explanatory variables. The explanatory variables to be included in the main regression analyses are:

- Age at CLOC screening
- Gender
- BMI

³ © SAS Institute Inc. https://documentation.sas.com/doc/no/pgmsascdc/v_016/statug/statug_freq_details70.htm, 18-Aug-2021

- Occupational status (employed/not employed?)
- Children at home (Y/N)
- Chronic disease (Y/N ≥ 1 chronic diseases)
- Dietary intake (Y/N)
 - Cod liver oil
 - Vitamin D
 - Omega 3
 - Fish consumers
- Present smoker (Y/N)

Other variables will be included in ad hoc/exploratory analyses.

The sample size in this study is so large that normal assumptions are likely to be valid. If this should not be appropriate for specific variables, appropriate non-parametric alternatives will be used. Should the assumptions to use Cox proportional hazard model not be satisfied, an alternative approach is logistic regression. The assumptions for methods used will be assessed. Should they be violated and not rectified by the sample size, alternative approaches will be used.

Sensitivity analyses will be conducted by including subsets of the study sample based on compliance. Other baseline variables may also be proposed as basis for ad hoc sensitivity analyses. Overdispersion will be considered for models where that can be an issue.

Further ad hoc subgroup analyses may be performed based on the findings of the primary analyses.

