Appendix 1: SAS variable names used in the received data set

The table below presents the SAS variable names as they appear in the original SAS data set received.

Variables	SAS variable names
Age group	
Gender	
Weight	
Height	
BMI	
Occupational status	
Education level	
Household income	
Household count	
Children living at home	
Smoking habits	
Chronic disease (Yes/No)	
Parents ethnic origin	
Skin type	
Sun exposure (July to October 2020)	
Dietary intake (Yes/No):	
Vitamin D supplement	
Omega-3 supplement	
Cod liver oil	
Fatty fish intake	
Compliance	
Airways infections	
SARS-CoV-2-tested	
Self-reported free-text side effects	
Laboratory measurements:	
Vitamin D	
Omega-3 index	
Baseline serology	

Primary variables:	
1. Serious COVID-19 (MSIS-confirmed COVID-19 with Dyspnoea, hospitalisation, or death)	CLOC_primary_1_severe_c19
2. COVID-19 defined by positive PCR obtained from MSIS	CLOC_primary_2_msis_status
3. A negative MSIS SARS-CoV-2 test	CLOC_primary_3_negative_tests
4. Self-reported airways infection	CLOC_primary_4_selfrep_airway

Description of the calculation of the four primary variables

- **First primary:** Serious COVID

- *CLOC_primary_1_severe_c19*

- Created by merging *deriv_sym_dyspnea_post_cov_yn_ever* and *deriv_hosp_post_cov_yn_ever* (see description below).
 - 1 = ever answered yes for dysp or hosp
 - 0 = only answered no for dysp or hosp
 - 999 = has filled out forms, has not answered for dysp or hosp question
 - NA = has not filled out forms / not tested positive (second primary)

- Only participants fulfilling the criteria for the second primary, will be included in this analysis. In addition, participants who have tested positive within one week after start of oil consumption are excluded from the analysis (*exclude_Msis_transtart7d*).

- Dyspnoea criteria

- Variable: *deriv_sym_dyspnea_post_cov_yn_ever*

- Answered dyspnoea in forms (R1-R6, E2, Q1) submitted after positive cov test (MSIS)
 - 1 = ever answered yes in any form
 - 0 = only answered no in any form
 - 999 = has filled out form, has not answered dypnoea question
 - NA = has not filled out form

- Hospitalized criteria

- Variable: *deriv_hosp_post_cov_yn_ever*

- Answered hospitalized because of COVID in forms (B1, B2, R1-R6, E2) submitted after positive cov test (MSIS)
 - 1 = ever answered yes in any form
 - 0 = only answered no in any form
 - 999 = has filled out form, has not answered hospitalized question

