 - NA = has not filled out form

- Death criteria

- Participant registered as dead/deceased in the National Population Register after a positive cov test (MSIS), but only if the death was related to COVID-19 based on hospital records or information from relatives.

- **Second primary:** New MSIS positive

- *CLOC_primary_2_msis_status*
 - Created from *MSIS_CLOC_test_status*
 - 1 = tested positive for the first time during **CLOC participation period**
 - 2 = only tested negative during **CLOC participation period** (never positive)
 - 3 = untested during **CLOC participation period** (never positive)
- Participants who have tested positive within one week after start of oil consumption are excluded from the analysis (*exclude_Msis_transtart7d*).
- MSIS criteria
 - Variable: *MSIS_CLOC_test_status*
 - 1 = tested positive for the first time during CLOC
 - 2 = only tested neg during CLOC (never positive)
 - *Variables obtained through MSIS (translated): “Test date” and “Test result”*
 - Variable to be analyzed as second primary endpoint identifying only tests registered during the **CLOC participation period** (defined as period from start of cod liver oil/placebo consumption (*deriv_Date_CLO_start_corr*) to June 2, 2021).
- **Third primary: Negative test**
 - *CLOC_primary_3_negative_tests*
 - Generated from *MSIS_CLOC_TotalTests_7d_neg*
 - Sum of total negative tests registered during the period from one week after start of cod liver oil/placebo consumption (*deriv_Date_CLO_start_corr*) to June 2, 2021.
 - 0 if no tests registered
 - Negative test criteria
 - Variable: *MSIS_CLOC_TotalTests_7d_neg*
 - Sum of total negative tests registered during the period from one week after start of cod liver oil/placebo consumption (*deriv_Date_CLO_start_corr*) to June 2, 2021.
 - Supplementary variables
 - *MSIS_CLOC_FirstNegative*
 - Date of first negative test registered during the **CLOC participation period**.
 - *MSIS_CLOC_LastNegative*
 - Date of last negative test registered during the **CLOC participation period**.
- **Forth primary: Self-reported airway infections**
 - *CLOC_primary_4_selfrep_airway*
 - Generated from *deriv_respinf_date_yn*
 - 1 = ever answered yes and provided valid date in any form
 - 0 = only answered no, or provided non-valid date in any form
 - 999 = has filled out form, has not answered airway infections question
 - NA = has not filled out form

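### SAP Appendix 1 restricts the first primary (serious COVID-19) to MSIS-positive participants, against the ITT denominator set in the SAP body and the protocol

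*SAP*

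**What the plan says.** The SAP body sets one analysis set for the primary variables. Section 4.2 states that "anyone who received bottles of cod liver/corn oil will participate in the primary" variables' analyses. Section 6.1 adds: "The primary analysis set is the defined ITT sample with missing data on outcome counting as the negative outcome". Section 6.3 treats the absence of a positive answer as No, and protocol section 9 (Analysis sets) agrees. Section 6.2 has the first, second and fourth primaries "analysed for relative risk (risk ratio) of acquiring a condition using cod liver oil versus corn oil" by a Wald test.

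Appendix 1, under the first primary, says something else: "Only participants fulfilling the criteria for the second primary, will be included in this analysis". The criterion for the second primary is a first MSIS-positive test during participation. The appendix then adds that "participants who have tested positive within one week after start of oil consumption are excluded from the analysis", and names a flag variable for this. The same week-one exclusion stands under the second primary.

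The variable for the first primary is built by merging a dyspnoea variable and a hospitalisation variable, both taken from forms submitted after the positive test. Its positive code reads "1 = ever answered yes for dysp or hosp". Participants who did not test positive are coded NA. A death criterion follows under the same heading, but neither the merge line nor any code refers to it.

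**The concern.** The documents give two denominators for the first test in the fallback sequence, so two analysts could follow this SAP and report different results from the same data. That test carries alpha 0.018 and decides whether the second primary is tested at 0.048 or 0.03 (SAP 4.1).

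The denominators answer different questions. The stated hypothesis is that the oil prevents serious COVID-19. Among MSIS-positives only, the risk ratio measures severity given infection. Infection happens after randomisation, is itself the second primary, and is assumed to fall with the oil. The groups compared would no longer be the randomised groups, and any benefit gained by preventing infection would be divided out of the ratio.

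The coding omission is a smaller matter. A participant who died of COVID-19 without submitting a form after the positive test would be NA on the merged variable, and then No under 6.3, although death is part of the endpoint.

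**Working it through.** **Inputs.** From SAP 3.3: serious COVID-19 incidence 0.25%, reduction 40%, alpha 0.018, power 70%, N 67,000; COVID-19 incidence 1%, reduction 20%, alpha 0.03, power 70%, N 65,000. Allocation is 1:1 (SAP 3.2), and the target is 80,000 (SAP 3.1). Sidedness is not stated, nor whether the incidences are placebo-arm risks. I assume two-sided tests and placebo-arm risks, because that reading reproduces the plan.

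**Step 1: the plan's N, with all participants as denominator.**

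N = 2 × [z(α/2)·√(2p̄(1−p̄)) + z(β)·√(p1(1−p1) + p2(1−p2))]² / (p1−p2)²

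- First primary: p1 = 0.0025, p2 = 0.0015, p̄ = 0.0020, z = 2.366 and 0.524. The bracket is 0.149465 + 0.033131 = 0.182596, and N = 2 × 0.182596² / 0.001² = 66,683 (plan: 67,000).
- Second primary: p1 = 0.010, p2 = 0.008, two-sided 0.03. N = 64,753 (plan: 65,000).
- Readings that miss: 0.25% and 1% as the mean over both arms give 53,319 and 58,219; a one-sided 0.018 gives 54,860 for the first primary.

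The sample size therefore rests on incidence among all participants.

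**Step 2: ITT power under the planned Wald test on the log risk ratio.** With 33,500 per arm, expected serious cases are 33,500 × 0.0025 = 83.75 and 33,500 × 0.0015 = 50.25.

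z = ln(0.60) / √(1/50.25 − 1/33,500 + 1/83.75 − 1/33,500) = −2.865

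Power = Φ(2.865 − 2.366) = 69%. With 40,000 per arm (100 and 60 cases), z = −3.131 and power is 78%.

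**Step 3: the same cases among positives only.** This joins the plan's two separate assumptions (infections cut by 20%, serious cases by 40%) and takes every serious case to be among the positives, as the definition requires. Positives at 67,000: 335 placebo and 268 oil. Risks: 83.75/335 = 25.0% and 50.25/268 = 18.75%, so RR = 0.75.

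z = ln(0.75) / √(1/50.25 − 1/268 + 1/83.75 − 1/335) = −1.815

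Power = Φ(1.815 − 2.366) = 29%. At 80,000 it is 35%.

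**Step 4: sensitivity to the fall in infections**, serious cases cut by 40% throughout. ITT power stays at 69% / 78%.

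| Fall in infections | Positives-only RR | Power at 67,000 / 80,000 |
|---|---|---|
| 0% | 0.60 | 79% / 87% |
| 5% | 0.63 | 69% / 78% |
| 10% | 0.67 | 57% / 66% |
| 20% | 0.75 | 29% / 35% |
| 30% | 0.86 | 8% / 10% |
| 40% | 1.00 | 0.9% / 0.9% (favouring oil) |

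The break-even is at a fall of about 5%. In simulated trials at the 20% fall, the two analyses disagree on significance in about 42% of trials at 67,000 and 44% at 80,000. Even at the 5% fall, where power is equal, they disagree in about 13% and 11%.

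**The case against.** The best defence is that Appendix 1 only documents the data set as received. A footnote in SAP 5.5 points to it for SAS variable names, and its codes are raw: the second primary is coded 1/2/3 and the fourth carries 999 and NA, although 6.1 wants Yes/No. On this view, NA for the uninfected becomes No under 6.3, and the ITT rule is untouched.

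Part of this stands. The NA code alone does not prove exclusion, and the body is consistent enough that ITT is the evident intent. A reader might infer that the plan has two equal versions, or that the sponsor has replaced its hypothesis with one on severity. The documents do not support that: hypothesis, method, analysis set and sample size all point to ITT.

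It does not dispose of the sentence itself, which says who is analysed, not how a value is coded. The next sentence does the same and names an exclusion flag. Elsewhere the appendix keeps uninfected participants when it means to: the second primary has codes for those only negative and those untested, and the third gives 0 to the untested. A programmer working from the appendix would build the wrong denominator.

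On death, a reader might infer that it was dropped from the endpoint. It was not: the row label and a separate criterion both include it. It is missing only from the merge line and the codes, and an attentive analyst might add it.

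A reader might also infer that the restriction always costs power. It does not, as Step 4 shows.

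**Conclusion.** The contradiction is real and must be resolved before unblinding, because it concerns the first confirmatory test. The change of question and the post-randomisation selection follow from the Appendix 1 sentence, if it is followed, whatever the effect sizes.

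The size depends on assumptions. With the plan's two reductions joined, placebo-arm base rates and two-sided 0.018, the risk ratio moves from 0.60 to 0.75, and power from 69% to 29% at 67,000 (78% to 35% at 80,000). The direction of the power effect depends on how far infections fall, so loss of power is an illustration and not the ground for the finding. The missing death code is a secondary omission; the documents give no rate from which to size it.

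**What to change.** Before unblinding:

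1. In Appendix 1, under the first primary, delete the sentence limiting the analysis to those who met the second primary and the week-one sentence after it. State instead that the first primary is analysed in the same set as the second, defined in 6.1.
2. In 6.1, define that set as the ITT population of 4.2, with one rule for week-one positives that is identical for primaries 1 and 2. Either keep them and code them 0, or leave them out of both and name the exception in 4.2 and 6.1. Make Appendix 1 match under both primaries. The choice matters little numerically: if infections spread evenly over 26 weeks (an assumption), it concerns about 335/26 = 13 placebo and 268/26 = 10 oil participants at 67,000. State there too how participants first positive before starting oil, and ITT members with no recorded start date, are handled, identically in both arms.
3. Code CLOC_primary_1_severe_c19 = 1 for a first MSIS-positive test from one week after deriv_Date_CLO_start_corr to June 2, 2021, plus any of: dyspnoea or hospitalisation as already derived from forms submitted after that test, or COVID-related death under the existing criterion, added to the merge. Code 0 for everyone else in the set, including those untested, those only negative, and positives with no severity answer and no COVID-related death. Reconcile the after-the-test form timing with protocol section 3, endpoint A, which requires dyspnoea or hospitalisation at the time of the positive test.
4. Report any positives-only severity analysis as supplementary, outside the fallback sequence.

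The cost is wording in Appendix 1 and 6.1 (and 4.2 if week-one positives are left out) plus one recode. No new data are needed.

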Sponsor and contact details

Sponsor: Oslo University Hospital, [name]

Principal Investigator (PI):

[name], PhD Oslo University Hospital, Department of Microbiology, Section of Research [name] Email: [contact] [contact]

Protocol Amendment Summary of Changes Table

DOCUMENT HISTORY			
Document	Date		
1.0: First complete REK approved protocol.	Completed October 5. Approved October 12, 2020		
1.01:	Completed October 22, 2020		
1.02	Completed October 27. 2020		
1.1	Completed November 30, 2020		

1.2	Completed November 10. 2021

Amendment 1 (October 22, 2020)

Use of antigen tests added as these have a very high specificity [18]. Change of full study title: addition of randomized, placebo and airway infections. Follow up period for definition of serious Covid-19 disease changed from 8 to 4 weeks.

Amendment 2 (October 27, 2020)

Norwegian label translated.

Endpoints described according to ClinicalTrials standard Endpoints at 12 months moved from secondary endpoints to exploratory endpoints.

Amendment 3 (November 30, 2020)

We have interpreted the Exclusion criteria about cod liver oil in Caucasians as Caucasians that use vitamin D cannot or cod liver oil 5-7 times per week can not be included, while use of omega 3 only is acceptable for inclusion. This is not directly clear from the text as it is written.

Amendment 4 (November 10, 2021)

Follow up period for definition of serious Covid-19 disease changed from 4 weeks to 'in the period around the positive SARS-CoV-2 test. Removed fever as an endpoint for serious Covid-19 disease. Primary endpoint 'laboratory verified respiratory infections' replaced with 'negative SARS-CoV-2 tests'. *'Laboratory verified respiratory infections' moved to secondary endpoints.*

Study compliance, blood sampling changed from monthly to after 3-4 months after start cod liver oil/placebo.

Simple dietary questions on vitamin D and LCPUFA n-3 food sources at baseline instead of a full FFQ. Definition of compliant participants changed.

Other minor changes.

1. Protocol Summary

Preliminary evidence from literature and an ongoing study in our lab suggests that cod liver oil may prevent Covid-19 and complications of Covid-19. We will investigate whether this is actually the case or in "Transtudien" by randomizing volunteers to take cod liver oil or placebo (corn oil) during the winter months of 2020-2021.

Schema

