cancer	difference in lung cancer incidence in	of vitamin D in cod
	postmenopausal women (RR 0.90, 95% CI 0.39 to	liver oil lung cancer
	2.08; 3 RCTs, 37601 women; low-certainty evidence).	indidence?

Benefit/Risk Assessment

Based on existing literature and data from Koronastudien, we have identified cod liver oil as a supplement that may prevent Covid-19 and or reduce the severity of the disease and found that the benefit of testing this in a randomized study far outweighs the risks. A full benefit/risk assessment is found in the Ethics section.

3. Objectives and endpoints

Based on the encouraging results from Koronastudien as well as existing evidence from the literature, we aim to investigate whether cod liver oil can prevent Covid-19, serious Covid-19, or other respiratory tract infections.

We also aim to explore and confirm already known health effects and possible new health effects, in particular rare adverse events associated with cod liver oil use. This will be done during a follow-up period of up to two years after the end of the cod liver oil period

We hypothesize that:

Intake of cod liver oil can prevent Covid-19 disease Intake of cod liver oil can prevent serious Covid-19 Intake of cod liver oil can prevent other airway infections

These hypotheses will be tested in a triple-blinded randomized placebo-controlled study where 80.000 participants will be assigned to cod liver oil or placebo in a 1:1 ratio.

The safety of cod liver oil will be explored.

Finally, it is a separate aim of the study to identify the mechanisms of action of any health effects seen.

Definition of endpoints

A. Number of participants diagnosed with serious Covid-19 (primary endpoint)

The number of participants with first time SARS-CoV-2 positive nasopharyngeal and or pharyngeal swabs (or any other sample used for detection of current disease) analyzed by reverse transcriptase quantitative polymerase chain reaction (RT-qPCR) nucleic acid amplification test or antigen tests [18] used by accredited Norwegian microbiology laboratories in the period from one week after the start of cod liver oil/placebo taking to the end of the study period together with any of the following:

A) Self-reported dyspnea concurrent with the positive test

OR

B) self-reported hospitalization caused by Covid-19 concurrent with the positive test OR

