Covid-19- related diagnoses and deaths in these registries are essential endpoints in the study and will be validated through inspection of the relevant hospital records (NPR) or hospital- or GP records (CDR). This will be done by contacting the hospital or GP for a copy of the relevant information from their records, which will be recorded in the CRF together with a conclusion about Covid-19 being the cause of the hospitalization or death. The information will also be presented for another independent and blinded physician for a second opinion, and in cases of discrepancy; the information will further be inspected by a blinded endpoint-verification committee for a final decision. It will be arranged for the endpoint-verification committee to have access to interview the treating physician.

The endpoint of subjective dyspnea during Covid-19 will be based on self-reporting (yes/no), but Covid-19 diagnosis is verified by the Norwegian Surveillance System for Communicable Diseases (MSIS).

Safety Assessment

Cod liver oil is recommended as a part of the Norwegian diet in official dietary recommendations and no safety assessment will be conducted during the cod liver oil/placebo taking period. See Ethics section.

Blood collection

Blood will be collected for the purpose of monitoring compliance and for the study itself. Blood will be collected according to the standard procedure described in Oslo University Hospitals' quality control system, and either venipuncture or dried blood spots will be used.

- Random blood collection for Compliance (either venipuncture or dried blood spot)
- Baseline and follow up for biobanking (either venipuncture or dried blood spot)
- Surplus material already stored in existing biobanks including treatment-biobanks will also be collected from the participants, and either stored in the study biobank or analyzed immediately (or both)

Blood samples will be analyzed for vitamin D levels (25(OH)D), EPA and DHA levels, and other biochemical parameters. The material will be stored in the study biobank for analyses to explore and explain the main results of the study. These analyses can include both biochemical, immunological, and molecular biology analyses and will be determined based on the results of the investigation.

Biobank

A study-specific biobank for the duration of the study until five years after all participants are dead will be created.

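### SAP Appendix 1 counts dyspnoea (and hospitalisation) reported on any form after the positive test, while the protocol requires it to be concurrent with the test, so the first primary can be diluted

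*SAP*

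**What the plan says.** **Protocol.** Section 3 (Definition of endpoints, A) requires a first positive test together with "Self-reported dyspnea concurrent with the positive test", or self-reported hospitalisation for Covid-19 that is likewise concurrent, or a Covid-related death. Section 8 (Endpoint Ascertainment and Validation) adds: "The endpoint of subjective dyspnea during Covid-19 will be based on self-reporting (yes/no"). The note on Amendment 4 describes the follow-up as "in the period around the positive SARS-CoV-2 test". No number of days is given in any of these places.

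**SAP.** Sections 3.3 and 6.1 name dyspnoea, hospitalisation or death without a time window, so Appendix 1 is the working rule. There the dyspnoea variable is described as "Answered dyspnoea in forms (R1-R6, E2, Q1) submitted after positive cov test (MSIS"), coded "1 = ever answered yes in any form". The hospitalisation variable is "Answered hospitalized because of COVID in forms (B1, B2, R1-R6, E2) submitted after positive cov test (MSIS"), with the same any-form coding. The composite is "1 = ever answered yes for dysp or hosp".

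**Elsewhere in Appendix 1.** Death counts only if related to COVID-19. The fourth primary needs a valid date between one week after the start of oil and 2 June 2021.

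**The concern.** This endpoint is tested first, at alpha 0.018. Its result also sets the level of the second test, 0.048 or 0.030 (SAP 4.1). Two current definitions of it exist, and they classify participants differently in three ways.

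- **Later events.** A participant with a mild infection in December who reports breathlessness in May meets the Appendix 1 rule but not the protocol's.
- **Earlier reports.** Dyspnoea on a form submitted shortly before the test date is concurrent in the protocol's sense, but Appendix 1 uses only forms submitted after the test.
- **Infection date.** Forms are monthly (protocol section 8), so an early infection is followed by more forms than a late one. A late case with no later form is coded NA, and missing outcomes count as negative (SAP 6.1 and 6.3).

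Dyspnoea is the most exposed component. As described, it has neither an attribution to COVID-19 nor a date limit. Hospitalisation lacks the time limit but is at least attributed.

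**Working it through.** **1. Is the conflict in current text?** Yes. The word concurrent stands in the protocol dated 10 November 2021, the date of the protocol that the SAP cites. SAP Amendment 1 (10 December 2021) aligned the endpoint period with the protocol but left this rule open-ended.

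**2. The plan's own figure.** Inputs from SAP 3.3: control incidence 0.25%, 40% reduction (0.15%), alpha 0.018, power 70%, 1:1. Sidedness is not stated; two-sided is assumed, so z = 2.366 and 0.524, with mean proportion 0.0020.

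n per arm = [2.366·√(2·0.0020·0.9980) + 0.524·√(0.0025·0.9975 + 0.0015·0.9985)]² / 0.0010² ≈ 33,342

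The total is 66,684, against 67,000 stated, and power at 67,000 is 70.2%. The sample size reproduces, so the problem is one of definition, not arithmetic.

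**3. Illustration of dilution.** Take the target of 80,000, or 40,000 per arm.

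- Positive tests: 1% and 0.8%, giving 400 vs 320.
- Truly serious: 0.25% and 0.15%, giving 100 vs 60 (RR 0.60).
- Positive but not serious: 300 vs 260.

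Assume that each later form has a chance q of an unrelated yes, independently between forms, and that every case has k later forms. Neither q nor k is in the documents. The share of non-serious cases counted is f = 1 − (1 − q)^k, and

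RR = (60 + 260f) / (100 + 300f).

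Power uses the Wald test on log RR, with SE = √(1/a + 1/b − 2/40,000) for a and b events. With no misclassification, SE = √(1/100 + 1/60 − 2/40,000) = 0.163 and |log 0.60| = 0.511. Then 0.511/0.163 − 2.366 = 0.765, giving power 78%.

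| k | q | f | Added cases | Events | RR | Power |
|---|---|---|---|---|---|---|
| – | 0 | 0 | 0 + 0 | 100 vs 60 | 0.60 | 78% |
| 3 | 1% | 0.030 | 9 + 8 | 109 vs 68 | 0.62 | 76% |
| 3 | 2% | 0.059 | 18 + 15 | 118 vs 75 | 0.64 | 75% |
| 3 | 5% | 0.143 | 43 + 37 | 143 vs 97 | 0.68 | 72% |
| 6 | 1% | 0.059 | 18 + 15 | 118 vs 75 | 0.64 | 75% |
| 6 | 2% | 0.114 | 34 + 30 | 134 vs 90 | 0.67 | 72% |
| 6 | 5% | 0.265 | 79 + 69 | 179 vs 129 | 0.72 | 69% |

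Six later monthly forms for every case is an upper bound, since it would need all infections to precede R1. The timing of E2 and Q1 is not defined.

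**4. Sensitivity to the infection effect.** If oil reduced severity but not infection (400 vs 400), then RR = (60 + 340f)/(100 + 300f). Three forms give RR 0.64-0.76 and power 70-42%; six give 0.68-0.84 and 62-23%. The plan assumes a 20% reduction in infection, so this is a departure from it, not the base case.

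**5. Dependence on infection date.** For q of 1% to 5%, the chance of at least one unrelated yes is 1-5% with one later form, 3-14% with three and 6-27% with six.

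**The case against.** **The question may be COVID-specific.** Appendix 1 gives a variable description, not the item wording. Protocol section 8 speaks of dyspnoea during Covid-19, and SAP 5.5 lists dyspnoea among COVID-positive participants; both fit an item tied to the infection. If it is so worded, most of the unrelated breathlessness disappears. This stands, and it is why the endpoint can, rather than does, pick up unrelated events. It does not remove the mismatch in time.

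**The protocol gives no number of days either.** Correct. Where to cut is partly judgement, but a rule with no limit cannot be read as concurrent.

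**The numbers are modest and assumed.** Also correct. On the plan's own effect sizes, power stays at 69-76% against a planned 70%. A reader might infer that the trial no longer answers the protocol's question about severity, or that a false positive becomes likelier. The documents support neither. Allocation is randomised and masked and one rule applies to both arms, so misclassification, including that linked to infection date, should be broadly balanced and should mainly dilute.

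**The denominator is disputed.** Appendix 1 restricts this analysis to participants who meet the second primary, whereas SAP 4.2 and 6.1 specify the ITT sample, used above. Among positives only, the starting ratio is (60/320)/(100/400) = 0.75. That is a separate inconsistency; dilution works in the same direction on either base.

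**Conclusion.** The conflict holds: following Appendix 1 yields a first primary endpoint that differs from the protocol's, for dyspnoea and for hospitalisation, and no other part of the SAP resolves it. The expected consequence is largely non-differential dilution. Illustratively, the risk ratio moves from 0.60 to 0.62-0.72 and power from 78% to 69-76%. This rests on an assumed 1-5% unrelated yes per form, independence between forms, three to six later forms for every case, and the plan's 20% reduction in infection. The true size cannot be calculated from the documents. This should be fixed before unblinding: confidence is high that the definitions differ, and medium on how much it matters.

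**What to change.** Before unblinding, reconcile Appendix 1 with protocol section 3:

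- Define concurrent as a pre-specified number of days around the MSIS test date, and record it in both documents.
- Redefine `deriv_sym_dyspnea_post_cov_yn_ever` to count dyspnoea only within that window, using every form, submitted before or after the test, whose reporting period overlaps it. Relying only on the form whose period contains the test date is not enough: it could miss dyspnoea later in the same episode, and capture would depend on where the test fell in the monthly cycle.
- Apply the same window to `deriv_hosp_post_cov_yn_ever`.
- Quote the wording of the dyspnoea item and state which forms qualify.
- Keep the open-ended version as a sensitivity analysis.

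The cost is the re-derivation of two variables from form dates and MSIS test dates that the current derivation already uses, and slightly fewer counted events. Monthly forms without a symptom date will leave some imprecision at the edges of the window. The stated sample size does not change.
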